How STDP and training might contribute to recovery of upper-limb and lower-limb function: The physiological basis for these protocols comes from animal studies showing that an increase or decrease in synaptic strength can be elicited by repeated pairs of presynaptic and postsynaptic action potentials that are precisely timed with respect to each other (Bi & Poo, 1998; Dan & Poo, 1998; Bi & Poo, 2001). If antidromic stimulation of a postsynaptic cell is paired with timed orthodromic stimulation of a presynaptic cell, bidirectional plasticity can be induced (Bi & Poo, 1998; Markram et al., 1997). In humans, corticospinal neurons can be activated by transcranial magnetic stimulation (TMS), and antidromic action potentials can be elicited in sensorimotor cortex and motoneurons by peripheral nerve/ spinal cord stimulation. STDP has been used successfully to precisely pair pulses to arrive at the spinal cord (Taylor & Martin, 2009). How to strengthen synaptic plasticity in corticospinal connections targeting the spinal cord (spinal synapses) of upper-limb and lower-limb muscles after SCI combined with training and its effect on voluntary output, remains unknown and will be investigated in this study.

STUDY ENDPOINTS:

The primary outcome measure utilized in this part of study is the Graded Redefined Assessment of Strength, Sensibility and Prehension (GRASSP see below). GRASSP is an extensive and validated impairment and functional measure which is able to detect subtle neurologic changes in individuals with spinal cord injury. Specifically, it evaluates the domains of sensation, strength, quality of different grip patterns and the ability to complete a variety of functional tasks.

The primary outcome measure utilized in this part of study the 10-meter Walk test. In the group receiving lower-limb exercises, we will use the 10-meter walk test to assess walking speed in meters per second. The same percentage of body-weight support will be used during pre- and post-assessments. A stopwatch will be used to measure the time to execute the task. The 10-meter walk will be repeated 3 times and the average will be used.

Participants may complete the following secondary endpoint measurements before and after the STDP protocol as outlined below.

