TMS and PNS/spinal root interstimulus interval (ISI). The ISI between TMS and PNS/spinal root stimulation will be set to allow descending volleys elicited by TMS to arrive at the presynaptic terminal of corticospinal neurons ~1-2 ms before antidromic PNS/spinal root volleys reach the motoneurons reach during STDP. The methods for timing the arrival of volleys at the spinal cord have been described previously (Bunday and Perez, 2012; Urbin et al., 2017; Bunday et al., 2018). Briefly, the ISI will be tailored to individual subjects based on conduction times calculated from latencies of MEPs, F-wave, and M-max. MEP latencies will be recorded during isometric ~10% of MVC of the target muscle to determine the shortest and clearest response for our estimations. The onset latency will be defined as the time when each response exceeds 2 SD of the mean rectified pre-stimulus activity (100 ms) in the averaged waveform. Peripheral conduction time (PCT) will be calculated using the following equation:

$$\text{PCT} = (\text{F-wave latency} - \text{M-max latency}) \times 0.5$$

Central conduction time (CTT) will be calculated using the following equation:

$$\text{CCT} = \text{MEP latency} - (\text{PCT} + \text{M-max latency})$$

Upper limb training

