If eligible, participants will be asked to complete pre, post, and follow-up assessment sessions in addition to the training sessions. Each assessment will require 2-5 sessions. Participants will complete up to 135 training sessions with a maximum of 360 paired pulses of stimulation and a small cohort of participants (n=10) will complete up to 270 training sessions with a maximum of 720 paired pulse of stimulation (up to 4 times per day). This will be determined based on preliminary data. In Aim 1, participants will be tested before and after at least 10 training sessions with single site stimulation. In Aim 2, participants will be tested before and after at least 40 training sessions with multisite stimulation. If a training session is not completed or missed participants will be asked to recover that session in a timely manner.

AIM 1: Randomized controlled design

Pre-assessment: 1. Physiology 2. Kinematics 3. Function	Stimulation Training + stimulation Training + sham stimulation	Post-assessment: 1. Physiology 2. Kinematics 3. Function	Follow-up assessment: 1. Physiology 2. Kinematics 3. Function
--	--	---	--

AIM 2:

Pre-assessment: 1. Physiology 2. Kinematics 3. Function	Training + stimulation	Post-assessment: 1. Physiology 2. Kinematics 3. Function	Follow-up assessment: 1. Physiology 2. Kinematics 3. Function
--	------------------------	---	--

We anticipate that each participant will take about 2-10 months to complete the study procedures/testing. Follow-up assessments will be done 1-9 months after completion of protocol, one follow-up in the first 3 months and the last follow-up in the 4-9 months following the last completed session. We will evaluate the subject's ability to move their hands, arms, legs, feet and/or toes using the different physiological and functional tests as mentioned above. TMS measurements, CMEPS and EMG recordings may also be done at these follow-up assessments.

INCLUSION AND EXCLUSION CRITERIA:

We anticipate the screening of 500 subjects across the two aims (60 subjects for Aim 1, and 40 for Aim 2) who have incomplete SCI at the cervical/thoracic/lumbar level (C2-L2). This number accounts for an attrition rate of 50%. To account for screen failures we would like to ask for a total of 200 subjects.

- Inclusion criteria for SCI subjects:
 - (1) Male and females between ages 18-85 years
 - (2) SCI at least 4 weeks post injury
 - (3) Spinal Cord injury at or above L2
 - (4) ASIA A,B,C, or D, complete or incomplete

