Aim 1: Repeated-measures ANOVA and Tukey post hoc analysis will determine effects of GROUP (stimulation, training+stimulation, and training+sham), TIME (before, immediately after, and follow-ups around 3 and 6 months post intervention) on physiological and behavioral outcomes. For alpha (type I error) of 0.05 and 1-beta (power) of 0.8, 45 SCI participants (15/group) will be included.

Aim 2: Repeated-measures ANOVA and Tukey post hoc analysis will determine effects training stimulation, TIME (before, immediately after, and follow-ups around 9 months post intervention) on physiological and behavioral outcomes. For alpha (type I error) of 0.05 and 1-beta (power) of 0.8, 11 SCI participants will be included.

Audio/Video Taping:

We plan to audio and video taping some parts of the experimental session, upon subject consent (optional in the consent form). Recordings will be only of the experimental activities described in the protocol. The subjects' identity will be hidden if subjects do not explicit consent to be recognized from the video or audio. The audio and video records will be stored in a password-protected file on a USB drive in a locked cabinet in the PI's office at the Rehabilitation Institute of Chicago.

The audio and video records will be used only for:

- a) Medical or scientific publications;
- b) Presentation at conferences;

The audio and video records will be destroyed after the time period chosen in the consent form.

This study does not involve any other risk to the subject, beyond some sense of effort and mild fatigue. Fatigue will be assessed based on the subjects' verbal report. They will be explicitly invited to interrupt the experiment if they experience fatigue. All studies will be carried out in the hospital environment where medical care is immediately available if needed.

POTENTIAL BENEFITS TO PARTICIPANTS:

Participation in the experiment may result in no direct improvement or, in the rare and unanticipated event, worsening of the subject's condition, including prolonged recovery time.

DATA MANAGEMENT AND CONFIDENTIALITY:

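### Physiological tests are left to discretion at every assessment, although the schema and the repeated-measures ANOVA treat physiology as part of each one

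*Combined protocol and SAP*

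**What the plan says.** Two statements make the tests permissive. Study Endpoints introduces the secondary battery, which contains the MEP, CMEP, F-wave, H-reflex and EMG/force tests, with "Participants may complete the following secondary endpoint measurements before and after the STDP protocol as outlined below". Study Timeline then says of the later visits: "TMS measurements, CMEPS and EMG recordings may also be done at these follow-up assessments".

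Three statements treat physiology as a regular part of the schedule.

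- The Study Timeline schema gives the content of the late visit, in both aims, as "Follow-up assessment: 1. Physiology 2. Kinematics 3. Function". The pre and post boxes list the same three domains.
- The sentence just before the permissive one says that the team will evaluate movement "using the different physiological and functional tests as mentioned above".
- Statistical Analysis specifies repeated-measures ANOVA. In Aim 1 the factor is "TIME (before, immediately after, and follow-ups around 3 and 6 months post intervention) on physiological and behavioral outcomes"; in Aim 2 it is "TIME (before, immediately after, and follow-ups around 9 months post intervention) on physiological and behavioral outcomes".

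The Aim 1 objective also commits the study to exploring training effects on physiological pathways and correlating them with hand and arm function. Physiology is therefore secondary, but it is a stated part of the aim and has a planned analysis.

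**The concern.** A repeated-measures ANOVA, as it is usually run, uses only people with a value at every time point. If staff may choose whether to run a test at a visit, the analysed set is whatever that choice leaves. The plan does not say who chooses, on what grounds, or what happens to a participant with a gap. Inclusion and Exclusion Criteria already allows for 50% attrition, so discretionary gaps would come on top of people who leave.

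Two things are at stake for the physiological results. The first is precision, because complete series may be few in groups of 15. The second is comparability: with no rule, testing could be more common in one arm than another, or among people whose responses are easy to record. The documents permit this; they do not say that it happens.

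**Working it through.** **The plan's own figure.** For Aim 1 the plan states: "For alpha (type I error) of 0.05 and 1-beta (power) of 0.8, 45 SCI participants (15/group) will be included". This cannot be reproduced, because no effect size, standard deviation, within-person correlation or named endpoint is given. Solving backwards, 45 people in three equal groups have 80% power in a one-way comparison for f = 0.48, so the noncentrality is N × f² = 45 × 0.48² ≈ 10.4. For Aim 2, 11 people have 80% power in a paired comparison for d = 0.94. These values serve below only as a scale.

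**Status of physiology, place by place.**

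| Assessment | Study Endpoints / Study Timeline text | Schema | ANOVA |
|---|---|---|---|
| Pre and post | whole secondary battery permissive | Physiology listed | both time points used |
| Follow-up | TMS, CMEP and EMG permissive; other tests covered only by the general sentence before | Physiology listed | about 3 and 6 months (Aim 1); about 9 months (Aim 2) |

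The text allows a test to be skipped at any of the four Aim 1 time points, while the analysis is written as if all four exist.

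**How many complete series might remain (Aim 1).** The documents give no uptake, so p, the share tested at each follow-up, is an assumption: 50% to 80%. Pre and post are taken as complete.

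- Independent uptake at two follow-ups, share complete = p²: 0.5² = 0.25, and 0.25 × 15 = 3.75; 0.8² = 0.64, and 0.64 × 15 = 9.6. That is about 4-10 of 15 per group.
- Same people tested both times, share complete = p: 0.5 × 15 = 7.5; 0.8 × 15 = 12. That is about 8-12 of 15.

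Uptake is probably correlated within a person, so the answer should lie between these two cases.

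If all four visits are discretionary and independent, the share is p⁴. With p = 0.9 this is 0.656, about 9.8 of 15. With p = 0.8 it is 0.410, about 6.1 of 15.

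**Illustrative loss of power.** Hold the effects at the back-solved values and drop incomplete series:

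| Share complete | Aim 1 N | Aim 1 power (f = 0.48) | Aim 2 n | Aim 2 power (d = 0.94) |
|---|---|---|---|---|
| 100% | 45 | 0.80 | 11 | 0.80 |
| 80% | 36 | 0.69 | 8.8 | 0.68 |
| 50% | 22.5 | 0.45 | 5.5 | 0.41 |

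This uses simple one-way and paired tests. The sponsor's actual calculation is unknown, so the table shows the direction and rough size only.

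**The case against.** The best reply is that the permissive wording introduces a long mixed menu of hand, arm, leg, spasticity and survey measures. It may mean only that not every test suits every participant. The schema names a domain and no particular test, so it can be met without an MEP at each visit. The sentence before the follow-up statement commits the team to physiological and functional tests, and everything at issue is secondary.

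Much of this stands. The schema does not require each test, and matching tests to the limb treated is sensible. But it does not settle the follow-up visits, where TMS, CMEP and EMG recordings are singled out as things that may be added. It also leaves the ANOVA without a defined set of outcomes measured on everyone.

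The numerical range is open to challenge too. The 50-80% has no source, and independence between visits sits badly with a worry that the same kinds of people are tested. For that reason both cases are shown.

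A reader might go further and infer that optional testing leaves some participants with no computable stimulation interval. The documents do not support that. The section on the interstimulus interval makes the recordings part of the intervention in its own right: "the ISI will be tailored to individual subjects based on conduction times calculated from latencies of MEPs, F-wave, and M-max", with MEP latencies to be recorded as a matter of course. The follow-up tests come after stimulation has ended. The listed nerve-stimulation targets include biceps and deltoid as well as hand muscles, so a participant without intrinsic hand contraction is not thereby left without an upper-limb target.

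**Conclusion.** The conflict is real and worth correcting, as a matter of moderate weight. Discretionary tests feed an analysis that presumes them at every time point, with no selection rule and no missing-data method. On an assumed 50-80% uptake per follow-up, complete Aim 1 series number about 4-10 of 15 per group under independence and about 8-12 of 15 if the same people are tested twice, with pre and post taken as complete. The physiological results could then describe a subset that might differ by arm.

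The point goes no further. Selection by response or tolerance is a risk and not a documented fact. A reader might also infer that the randomised comparison is biased because unrecordable responses come to light only after allocation. No text puts the check there, and the Aim 1 schema shows a pre-assessment with physiology ahead of the three arms. GRASSP and the 10-meter walk test, the primary endpoints, lie outside the permissive wording and are not affected.

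**What to change.** 1. In Study Endpoints and Study Timeline, replace *may* with *will* for a short core set: MEP, F-wave/M-max, and EMG/force during MVC of the target muscle. Require it at pre, post and both follow-ups in all arms, including sham.
2. In Statistical Analysis, analyse the core set with a mixed model that uses all available visits, and state its missing-data assumption.
3. Keep the remaining tests optional and report them descriptively.

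As a separate, minor clarification, state that the latencies used to set the interval are obtained at pre-assessment, before allocation, in every Aim 1 arm.

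The cost is protocol wording and somewhat longer follow-up visits. The core tests are already in the battery, and each assessment already allows 2-5 sessions.

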During stair climbing, subjects will climb up and down 4 steps with 3 full repetitions. Locomotor training+STDP protocol: In each session, STDP stimulation will be targeting the leg muscles at rest, and their effects will be tested on voluntary contractions. Locomotor training will be preceded by the STDP protocol. The locomotor training will consist of walking. The amount of weight support will be provided as needed by a body-weight support system and the level of support will be associated with gait kinematics which resemble unsupported walking. The body-weight support system is a robotic over ground arrangement for practicing a wide range of activities without the risk of falling. The support will be adjusted within and between sessions as necessary to prevent excessive knee flexion during stance phase or toe dragging during swing phase (Finch et al., 1991). Subjects will be encouraged to walk at their comfortable speed at which step kinematics are acceptable (no toe dragging, an adequate knee flexion during swing phase, adequate knee extension at initial stance phase, etc.). All subjects will be allowed to rest as needed during the training sessions. The starting and end points and guiding path will be marked with lines on the floor. Thirty five retro-reflective markers will be attached to the participant's body according to the Plug-In-Gait market set. While the participant is walking on the path, joint movements will be acquired by a 3dimensional motion capture system. The locomotor training session will consist of at least 3 sessions are expected to be completed per week as the participant is able. Missed sessions will be rescheduled according to the subject's availability.

STUDY TIMELINE:

Participants will be initially screened over the phone or in person to ensure eligibility based on established inclusion and exclusion criteria.

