 - (5) Possess the following abilities
 - (Aim 1) The ability to produce a visible precision grip force with one hand, and/or the ability to perform some small wrist flexion and extension (Aim 2) The ability to perform a small visible contraction with dorsiflexion and hip flexor muscles

- Exclusion criteria for SCI Subjects:
 - (1) Uncontrolled medical problems including pulmonary, cardiovascular or orthopedic disease
 - (2) Any debilitating disease prior to the SCI that caused exercise intolerance
 - (3) Premorbid, ongoing major depression or psychosis, altered cognitive status
 - (4) History of head injury or stroke
 - (5) Vascular, traumatic, tumoral, infectious, or metabolic lesion of the brain, even without history of seizure, and without anticonvulsant medication
 - (6) History of seizures or epilepsy
 - (7) Receiving drugs acting primarily on the central nervous system, which lower the seizure threshold (see appendix 2)
 - (8) Pregnant females
 - (9) Ongoing cord compression or a syrinx in the spinal cord or who suffer from a spinal cord disease such as spinal stenosis, spina bifida, MS, or herniated disk
 - (10) Metal plate in skull
 - (11) Individuals with scalp shrapnel, cochlear implants, or aneurysm clips

RECRUITMENT METHODS:

We anticipate screening of 500 subjects to complete the study (see description above). We will be using the IRB approved SCI registry for recruitment. A letter granting access to the registry is included in the submission. Subjects who have previously expressed an interest in participating in research studies at the Shirley Ryan AbilityLab complete a questionnaire and request that their information be entered into the research volunteer database. This database is searchable based on criteria such as age, time-post injury and injury level. Potential subjects will be called by the study coordinator. If the individuals have not agreed to be contacted by phone for future studies then the treating physician will be the one contacting them. The phone call will be to provide information about the study to the individual to determine if they are interested in the study. We will not be collecting any information from the individual. All the screening will be done after written consent is collected and before enrollment.

COMPENSATION FOR PARTICIPATION IN RESEARCH ACTIVITIES:

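### The recruitment total is given as both 500 and 200, and the 50% attrition is tied to no named number, so it is unclear whether Aim 1 keeps its 45

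*Combined protocol and SAP*

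**What the plan says.** All places are in the combined protocol and SAP.

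- **Cover page:** the sample-size field reads 500.
- **Inclusion and Exclusion Criteria**, opening paragraph, three sentences in this order. First: "We anticipate the screening of 500 subjects across the two aims (60 subjects for Aim 1, and 40 for Aim 2". Second: "This number accounts for an attrition rate of 50" per cent. Third: "To account for screen failures we would like to ask for a total of 200 subjects".
- **Recruitment Methods:** "We anticipate screening of 500 subjects to complete the study". The same section says of the volunteer database: "This database is searchable based on criteria such as age, time-post injury and injury level". Of the telephone call it says: "We will not be collecting any information from the individual". It then adds: "All the screening will be done after written consent is collected and before enrollment".
- **Study Timeline:** "Participants will be initially screened over the phone or in person to ensure eligibility".
- **Statistical Analysis:** alpha 0.05 and power 0.8 are linked to 45 participants (15 per group) for Aim 1 and to 11 for Aim 2. No effect size or standard deviation is given. Nor does the section say whether 45 and 11 are people enrolled or people completing.

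**The concern.** Two things cannot be read from the text.

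The first is the recruitment total. Someone who fails screening has been screened, so a total meant to allow for screen failures is a count of people screened. The Inclusion section therefore offers two such counts, 500 and 200, together with per-aim numbers that add to 100.

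The second is the number expected to finish. The attrition sentence points back to a number without naming it. The candidates already on the page at that point are 500, the pair 60 and 40, and their sum of 100. Aim 1 is the randomised three-group comparison. Whether it keeps the 45 on which its stated power rests depends on whether 60 is counted before or after half the participants are lost.

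**Working it through.** **Inputs.** 500 (cover page, Inclusion, Recruitment Methods); 60, 40, 50% and 200 (Inclusion); 45 and 11 (Statistical Analysis). The 45 and 11 cannot be re-derived, because no effect size or standard deviation is given. The check is whether the recruitment figures follow from them or from each other.

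**1. Inflate the analysis numbers for 50% attrition**, using n / (1 − d):
- Aim 1: 45 / 0.5 = 90
- Aim 2: 11 / 0.5 = 22
- Both: 56 / 0.5 = 112

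None of these is 60, 40, 100, 200 or 500. The common shortcut n × (1 + d) gives 68, 17 and 84, which do not match either.

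**2. Work backwards.** Going from 60 to 45 implies attrition of 1 − 45/60 = 25%. Going from 40 to 11 implies 1 − 11/40 = 72.5%. Neither is 50%.

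**3. Look for any link among the recruitment figures.** The only match is 100 / (1 − 0.5) = 200, but the text attributes 200 to screen failures, not to attrition. No inflation gives 500.

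**4. Try to build a complete chain.** The screening losses below are implied by the figures; the plan states no screen-failure rate.

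| | Screened | Enrolled | Completing | What does not fit |
|---|---|---|---|---|
| Reading A | 200 | 60 + 40 = 100 | 30 + 20 = 50 | The 500 screened has no place |
| Reading B | 500 | 200 | 60 + 40 = 100 | The 200 is not a screen-failure total, and the attrition sentence would have to refer to a 200 not yet mentioned |

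The cover-page sample size of 500 matches enrolment on neither reading (100 or 200).

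**5. Compare completers with the analysis numbers.**
- Aim 1: 60 × 0.5 = 30 on A, below 45 by 15; 60 on B, above 45.
- Aim 2: 40 × 0.5 = 20 on A; 40 on B; both above 11.

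**6. Illustrate what 30 against 45 could mean.** Assumptions: one-way ANOVA with three groups, alpha 0.05, and a lost participant contributes no data. The effect is back-solved so that 45 gives exactly 80%, which yields f = 0.480 (f² = 0.2301). Noncentrality is N × f².

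| N | Noncentrality | Power |
|---|---|---|
| 45 | 45 × 0.2301 = 10.4 | 80.0% (by construction) |
| 30 | 30 × 0.2301 = 6.9 | 59.7% |
| 60 | 60 × 0.2301 = 13.8 | 91.0% |

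The plan specifies repeated measures. Back-solving in the same way for the group-by-time term (three groups, four times, sphericity assumed) gives 58.0% at 30 and 91.7% at 60, so the picture does not depend on the simpler model.

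**The case against.** The best defence is that 500 and 200 count different people: 500 looked at before consent and 200 consented. The searchable database and the phone or in-person screen in Study Timeline make this conceivable. However, the document never calls the database search screening, and Recruitment Methods places all screening after written consent and says that the call gathers nothing. As written, the defence is a guess. A reader could also note that 500 appears three times and 200 once, so 500 is the dominant figure. That is true, but it leaves the 200 sentence wrong or mislabelled.

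Three stronger inferences are not supported.

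- *Aim 1 is underpowered.* The shortfall exists only if 60 is enrolment before attrition, which the text does not say. The power figures also rest on an invented effect size and on total loss of data from everyone who drops out, including those lost only at late follow-up. The documented comparison is 30 against 45, on one reading.
- *Half of 45 will be lost, leaving 22 or 23.* This belongs to neither reading, since the plan gives 60 for Aim 1.
- *Study Timeline and Recruitment Methods contradict each other on when screening occurs.* Study Timeline does not mention consent and does not say that its phone screen is the recruitment call. A phone or in-person screen after consent would satisfy both sections. This is an ambiguity that bears on what the 500 counts.

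**Conclusion.** The concern holds for the two central points. The 500 screened and the total of 200 covering screen failures cannot both stand as labelled, and the number that carries the 50% attrition is not identified. Neither conclusion needs any assumption beyond the ordinary meaning of screening and screen failure.

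The consequence for the randomised comparison is conditional. Aim 1 has either 30 completers, with illustrative power near 60%, or 60 completers and no shortfall. Readings A and B are reconstructions; neither fits all the labels, and the text does not settle which was meant. Because the expected number of completers in the randomised aim cannot be determined, the wording should be corrected before the stated 80% is relied on.

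**What to change.** 1. For each aim, state one chain: screened, enrolled or randomised, completing. Use it on the cover page and under Inclusion and Exclusion Criteria, Recruitment Methods and Statistical Analysis.
2. Correct or relabel the 500 and the 200 to match that chain.
3. Name the number to which the 50% attrition applies.
4. In Statistical Analysis, say whether 45 and 11 are enrolled or completing.
5. If 60 is enrolment before attrition, restate Aim 1 power for 30 completers. If it is the number after attrition, say so and correct the sentence that attributes 200 to screen failures.
6. As a secondary wording point, reconcile Study Timeline with Recruitment Methods so that it is clear whether the 500 are counted before or after consent.

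The cost is protocol wording and, if 60 proves to be a pre-attrition figure, a less favourable stated power for Aim 1. Settling between 500 and 200 may also change the recruitment total on record.
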